3 ABBREVIATIONS

Abbreviations pertain to the SAP only (not the TFLs).

ADaM	analysis data model
A_e	Amount of drug excreted unchanged in urine
AE	adverse event
$AUC_{0-\tau}$	Area under the plasma concentration-time curve over a dosing interval ($\tau = 12$ hours)
AUC_{0-last}	Area under the plasma concentration-time curve from time zero to the time of the last quantifiable concentration
$AUC_{0-\infty}$	Area under the plasma concentration-time curve from time zero to infinity
$\%AUC_{extrap}$	Area under the plasma concentration-time curve extrapolated from last quantifiable concentration to infinity as a percentage of total AUC
BID	twice daily
BLQ	below the level of quantification
CDISC	Clinical Data Interchange Standards Consortium
CI	Confidence interval
CL/F	Apparent total plasma clearance
CL_R	Renal clearance
C_{max}	Maximum observed plasma concentration
C_{min}	Minimum observed plasma concentration
CRF	Case Report Form
CRU	Clinical Research Unit
CSR	Clinical Study Report
CV%	coefficient of variation
EC	Early Clinical
ECG	electrocardiogram
f_e	Percentage of dose excreted unchanged in urine
ICH	International Conference on Harmonisation
LLOQ	lower limit of quantification

MedDRA	Medical Dictionary for Regulatory Activities
NASH	Nonalcoholic Steatohepatitis
NC	Not calculated
NR	No result
PK	pharmacokinetic
QTc	QT correction; QT interval corrected for heart rate
QTcB	QTc calculated using the Bazett correction
QTcF	QTc calculated using the Fridericia correction
RA _{AUC0-τ}	Observed accumulation ratio based on AUC _{0-τ}
RA _{C_{max}}	Observed accumulation ratio based on C _{max}
SAP	Statistical Analysis Plan
TBD	To be determined
TEAE	treatment-emergent adverse event
TFLs	tables, figures, and listings
t _{1/2}	Apparent plasma terminal elimination half-life
T _{max}	Time of the maximum observed plasma concentration
Vz/F	Apparent volume of distribution during the terminal elimination phase

4 INTRODUCTION

This SAP has been developed after review of the clinical study protocol (Final Version 2.0 dated 05 November 2018).

This SAP describes the planned analysis of the safety, tolerability, PK, and biomarker data from this study. A detailed description of the planned TFLs to be presented in the Clinical Study Report (CSR) is provided in the accompanying TFL shell document.

The intent of this document is to provide guidance for the statistical analyses of PK and Biomarker data. In general, the analyses are based on information from the protocol, unless they have been modified by agreement between Galecto Biotech and Covance Early Clinical (EC) Biometrics. A limited amount of information concerning this study (eg, objectives, study design) is given to help the reader's interpretation. This SAP must be finalised prior to the lock of the clinical database for this study. When the SAP and TFL shells are agreed upon and finalised, they will serve as the template for this study's CSR.

This SAP supersedes the statistical considerations identified in the protocol; where considerations are substantially different, they will be so identified. If additional analyses are required to supplement the planned analyses described in this SAP, they may be performed and will be identified in the CSR. Any substantial deviations from this SAP will be agreed upon between Galecto Biotech and Covance EC Biometrics and identified in the CSR.

This SAP is written with consideration of the recommendations outlined in the International Conference on Harmonisation (ICH) E9 guideline entitled, "Guidance for Industry: Statistical Principles for Clinical Trials" and the ICH E3 guideline entitled, "Guidance for Industry: Structure and Content of Clinical Study Reports."^{1,2}

5 STUDY OBJECTIVES

The primary objectives of the study are:

- to evaluate the safety and tolerability of single and multiple doses of GB1211 administered to healthy subjects.
- to evaluate the safety and tolerability of multiple doses of GB1211 administered to subjects with suspected NASH and liver fibrosis.

The secondary objectives of the study are:

- to evaluate the PK of single doses of GB1211 in plasma and urine in healthy subjects and the PK of multiple doses of GB1211 in plasma of healthy subjects and subjects with suspected NASH and liver fibrosis.
- to determine the effect of food on the single oral dose PK of GB1211.

The exploratory objectives of the study are:

- to investigate biomarkers related to GB1211 activity at single and/or multiple doses in comparison to placebo in healthy subjects and subjects with suspected NASH and liver fibrosis.
- to investigate biomarkers of metabolism, inflammation, and fibrosis following multiple doses of GB1211 in healthy subjects and/or subjects with suspected NASH and liver fibrosis.
- to identify metabolites of GB1211 in plasma and urine.

6 STUDY DESIGN

6.1 Part A

Part A will comprise a single-dose, sequential-cohort study incorporating a single-cohort, randomised, 2-part arm to investigate the effect of food. Overall, 40 subjects will be studied in 5 cohorts (Cohorts A1 to A5), with each cohort consisting of 8 subjects.

Potential subjects will be screened to assess their eligibility to enter the study within 28 days prior to the first dose administration. Each subject will participate in 1 treatment period only, residing at the Clinical Research Unit (CRU) from Day -1 (the day before dosing) to Day 3 (48 hours postdose), except for the food-effect cohort (planned to be Cohort A3), where each subject will participate in 2 treatment periods separated by a minimum of 7 days.

All subjects will return for a Follow-up visit 5 to 7 days after their final dose.

Dose Regimen:

[figure not shown]
In each of Cohorts A1 to A5, 6 subjects will receive GB1211 and 2 will receive placebo. In all cohorts, except the food-effect cohort, all doses will be administered in the fasted state in accordance with a randomisation schedule on the morning of Day 1. For the food-effect cohort, which is planned to be Cohort A3, Treatment Period 1, Day 1 doses will be administered in the fasted state in accordance with the randomisation schedule and in Treatment Period 2, Day 1 doses will be given 30 minutes after the start of a high fat breakfast. Each subject in Cohorts A1 to A5 (except the food-effect cohort) will receive only a single dose of GB1211 or placebo during the study. In the food-effect cohort, subjects will receive the same treatment in both periods and will receive 2 single doses of GB1211 or placebo during the study.

In Cohorts A1 to A5 (except the fed period of the food-effect cohort), dosing will occur such that 2 subjects (1 active and 1 placebo) will be dosed at least 24 hours before the remaining subjects, where continuation to dose the remaining subjects will be at the Investigator's discretion.

Based on the ongoing review of the safety, tolerability, and PK results, additional nonresidential visits may be required. The number of additional visits per subject will not exceed 3 and will not extend beyond 28 days after each final dosing occasion.

[figure not shown]
An overview of the study design is shown in [Figure 1](#) and [Figure 2](#) and the planned dose levels in [Figure 3](#).

Figure 1: Study Schematic - Part A Cohorts (Except the Food-Effect Cohort)

[figure not shown]
Abbreviation: CRU = Clinical Research Unit

Figure 2: Study Schematic - Part A Food-Effect Cohort (Planned to be Cohort A3)

Abbreviation: CRU = Clinical Research Unit

Figure 3: Planned Dose Levels (Part A)

The total duration of study participation for each subject (from Screening through Follow-up visit) for all Part A cohorts except the food-effect cohort is anticipated to be approximately 5 weeks. For each subject in the food-effect cohort (planned to be Cohort A3), the total duration is anticipated to be approximately 6 to 7 weeks.

6.2 Part B

Part B will comprise a multiple-dose, sequential-cohort study. Overall, 22 subjects will be studied in 2 cohorts (Cohorts B1 to B2), with each cohort consisting of 11 subjects. Dosing in Part B will start following review of safety, tolerability, and PK data from a single dose with exposure higher than the predicted steady-state exposure.

Potential subjects will be screened to assess their eligibility to enter the study within 28 days prior to the first dose administration. Each subject will participate in 1 treatment period only and reside at the CRU from Day -1 (the day before dosing) until the morning of Day 11 (24 hours after the final dose on Day 10).

All subjects will return for a Follow-up visit 5 to 7 days after their final dose.

[figure not shown]
Dose Regimen:

In each of Cohorts B1 to B2, 8 subjects will receive GB1211 and 3 subjects will receive placebo. The dietary state for dosing in Part B will be fasted unless data from the food-effect cohort is

available and supports dosing in the fed state. For all subjects, the planned dosing will be BID on Days 1 to 9, inclusive, and a final single dose administration will occur in the morning of Day 10. The dosing interval/frequency and dosing duration in Part B may be changed following review of data from cohorts in Part A. The predicted total daily exposure will not exceed the highest exposure observed in Part A. There will be a minimum of 10 days between dose escalations for each cohort.

[figure not shown]
An overview of the study design is shown in [Figure 4](#) and the planned dose levels in [Figure 5](#).

Figure 4: Study Schematic (Part B)

Abbreviations: BID = twice-daily; CRU = Clinical Research Unit

Figure 5: Planned Dose Levels (Part B)

Abbreviations: BID = twice-daily; TBD = to be determined

The total duration of study participation for each subject (from Screening through Follow-up visit) is anticipated to be approximately 6 to 7 weeks.

6.3 Part C (Optional)

Part C will comprise a multiple-dose cohort of 25 subjects with suspected NASH and liver fibrosis (Cohort C1). Part C may start following review of data from Part A and at least 1 Part B cohort.

Potential subjects will be screened to assess their eligibility to enter the study within 28 days prior to the first dose administration. Each subject will participate in 1 treatment period only and reside at the CRU from Day -1 (the day before dosing) until the morning of Day 2, returning for nonresidential visits on Days 7, 14, 21, 28, and 35. Subjects will then check back into the CRU on Day 41 until the morning of Day 43 (24 hours after the final dose on Day 42).

[figure not shown]
All subjects will return for a Follow-up visit 5 to 7 days after their final dose.

Dose Regimen:

For Part C, Cohort C1, 15 subjects will receive GB1211 and 10 subjects will receive placebo. The dietary state for dosing in Part C will be fasted unless data from the food-effect cohort is available and supports dosing in the fed state. For all subjects, the planned dosing will be BID on Days 1 to 41 inclusive, and a final single dose administration will occur in the morning of Day 42. The total daily dose administered, dose interval/frequency, and dosing duration will be based on review of data from Parts A and B.

An overview of the study design is shown in [Figure 6](#).

Figure 6: Study Schematic (Part C)

Abbreviations: BID = twice-daily; CRU = Clinical Research Unit

The dose level of Part C is to be determined following completion of Part A and at least 1 cohort of Part B.

The total duration of study participation for each subject (from Screening through Follow-up visit) for Cohort C1 is anticipated to be approximately 11 weeks.

This SAP and the accompanying shells are related to the analysis of Parts A and B only.

7 TREATMENTS

The following is a list of the study treatment abbreviations and ordering that will be used in the TFLs.

Part	Study Treatment Name	Treatment Order on TFLs
A	Placebo (fasted)	1
	Placebo (fed)	2
	5 mg GB1211 (fasted)	3
	20 mg GB1211 (fasted)	4
	50 mg (10 x 5 mg) GB1211 (fasted)	5
	50 mg (1 x 50 mg) GB1211 (fasted)	6
	50 mg (1 x 50 mg) GB1211 (fed)	7
	100 mg GB1211 (fasted)	8
	200 mg GB1211 (fasted)	9
	400 mg GB1211 (fasted)	10
B	Placebo bid	11
	50 mg GB1211 bid	12
	100 mg GB1211 bid	13

8 SAMPLE SIZE JUSTIFICATION

No formal statistical assessment, in terms of sample size, has been conducted as this is the first time GB1211 is being administered to humans. However, the number of subjects in each part of the present study is common in early clinical pharmacology studies and is considered sufficient to achieve the objectives of the study.

9 DEFINITION OF ANALYSIS POPULATIONS

The **Safety Population** will consist of all subjects who received at least 1 dose of study drug (GB1211 or placebo).

The **PK population** will include all subjects who received at least 1 dose of GB1211 and have evaluable PK data. A subject may be excluded from the PK summary statistics and statistical analysis if the subject has an AE of vomiting that occurs at or before 2-times median time to maximum concentration.

The **Biomarker Population** will include all subjects who received at least 1 dose of study treatment (GB1211 or placebo) and have at least 1 postdose biomarker assessment.

All protocol deviations that occur during the study will be considered prior to database lock for their severity/impact and will be taken into consideration when subjects are assigned to analysis populations. Details of subject assignment to the analysis populations will be listed.

The **All Subjects Population** will consist of any subjects who signed informed consent and had study assessments recorded on the database as per the protocol.

10 STATISTICAL METHODOLOGY

10.1 General

Data listings will be provided for the All Subjects Population. Summary statistics and statistical analyses will be performed for subjects included in the relevant analysis populations (Safety/PK/Biomarker).

For continuous data, summary statistics will include the arithmetic mean, arithmetic standard deviation, median, minimum, maximum, and number. For log-normal data (eg, the PK parameters: areas under the concentration-time curve [AUCs] and maximum observed concentration [C_{max}]), the geometric mean and geometric coefficient of variation (CV%) will also be presented. For categorical data, frequency counts and percentages will be presented. Data listings will be provided for all subjects up to the point of withdrawal, with any subjects excluded from the relevant population highlighted. For the calculation of summary statistics and statistical analysis, unrounded data will be used.

Missing values will not be imputed.

Data analysis will be performed using SAS[®] Version 9.4 or later.

Analysis Data Model (ADaM) datasets will be prepared using Clinical Data Interchange Standards Consortium (CDISC) ADaM Version 2.1, and CDISC ADaM Implementation Guide Version 1.1. Pinnacle 21 Community Validator Version 2.2.0 will be utilised to ensure compliance with CDISC standards.

10.1.1 Definition of Baseline and Change from Baseline

Baseline for each parameter is defined as the last value measured prior to dosing, including repeat (vital signs and electrocardiograms [ECGs]) and unscheduled (clinical laboratory parameters) readings (see [Section 10.1.2](#) for definitions of repeat and unscheduled readings). For vital signs taken in triplicate, baseline will be the median of the last 3 values taken prior to dosing (pre-am dosing for multiple dose parts). For ECGs taken in triplicate, baseline will be the mean of the last 3 values taken prior to dosing (pre-am dosing for multiple dose parts).

Mean change from baseline is the mean of all individual subjects' change from baseline values. Each individual change from baseline will be calculated by subtracting the individual subject's baseline value from the value at the timepoint. The individual subject's change from baseline values will be used to calculate the mean change from baseline using a SAS procedure such as Proc Univariate.

10.1.2 Repeat and Unscheduled Readings

Repeat readings occur when the original vital signs or ECG result requires confirmation. Repeat readings are labelled as 'Repeat' in the listings and replace the original readings in all summaries and changes from baseline presentations and calculations. Prior to dosing, all readings taken in addition to the original reading are defined as predose repeats. Postdose repeat readings are defined as readings collected within 15 minutes of the actual time of the original reading. Where results are taken in triplicate and repeated, the last 3 readings are used in all subsequent calculations.

With the exception of predose results described above, unscheduled readings for vital signs or ECGs are defined as readings collected >15 minutes from the actual time of the original reading. Where results are taken in triplicate, the original reading is defined as the first reading of the triplicate. All results not taken at a scheduled timepoint for other data types (eg, clinical laboratory parameters) are unscheduled. Unscheduled readings are labelled as 'Unscheduled' in the listings. Because unscheduled readings are not associated with any scheduled timepoint, they are excluded from all summaries (with the exception that they may be used as baseline, as stated in [Section 10.1.1](#)).

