7.3.3. Vital Signs

Supine blood pressure, supine pulse rate, and oral body temperature will be assessed at the times indicated in the Schedule of Assessments in [Appendix 6](#). Vital signs may also be performed at other times if judged to be clinically appropriate or if the ongoing review of the data suggests a more detailed assessment of vital signs is required.

Day 1 predose blood pressure and pulse rate will be measured in triplicate at approximately 2-minute intervals. The median value will be used as the baseline value in the data analysis. All subsequent measurements will be performed singly and repeated once if outside the relevant clinical reference ranges. Oral body temperature will be measured singly.

Subjects must be supine for at least 5 minutes before blood pressure and pulse rate measurements.

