7.3.4. Electrocardiogram

7.3.4.1. 12-Lead Electrocardiogram

Resting 12-lead ECGs will be recorded after the subject has been supine and at rest for at least 5 minutes at the times indicated in the Schedule of Assessments in [Appendix 6](#). Single 12-lead ECGs will be repeated once if either of the following criteria apply:

- QTcF value > 500 msec
- QTcF change from the baseline (predose) is > 60 msec.

Additional 12-lead ECGs may be performed at other times if judged to be clinically appropriate or if the ongoing review of the data suggests a more detailed assessment of ECGs is required. The Investigator (or designee) will perform a clinical assessment of each 12-lead ECG.

Day 1 predose 12-lead ECGs will be measured in triplicate at approximately 2-minute intervals. The mean value will be used as the baseline value in the data analysis. All subsequent measurements will be performed singly and repeated once if outside the relevant clinical reference ranges.

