10.6.2 Clinical Laboratory Parameters

Serum biochemistry and haematology data will be summarised by treatment. Changes from baseline will be calculated. In addition, all serum biochemistry, haematology, and urinalysis data outside the clinical reference ranges will be listed by parameter and treatment.

Values for any serum biochemistry, haematology, and urinalysis values outside the clinical reference ranges will be flagged on the individual subject data listings.

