10.6.3 Vital Signs

Where vital signs are measured in triplicate (at approximately 2-minute intervals), the median value will be used in all subsequent calculations. Changes from baseline will be calculated.

Vital signs values outside the clinical reference ranges will be flagged on the individual subject data listings.

The vital signs data will be summarised by treatment, together with changes from baseline. Figures of mean vital signs and mean change from baseline profiles will be presented by treatment.

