10.6.4 Electrocardiogram

The ECG data will be obtained directly from the 12-lead ECG traces. These data include the QT interval calculated using the Bazett correction (QTcB), the QT interval calculated using the Fridericia correction (QTcF), the PR and QT intervals, the QRS duration, and heart rate.

Where ECGs are measured in triplicate (at approximately 2-minute intervals), the mean value will be used in all subsequent calculations. Changes from baseline will be calculated.

Values for ECG parameters outside the clinical reference ranges will be flagged on the individual subject data listings.

The ECG data will be summarised by treatment, together with changes from baseline. Figures of mean ECG data and mean change from baseline profiles will be presented by treatment.

An outlier analysis will be performed including all individual postdose measurements (not the mean data), including all repeat and unscheduled readings. The frequency of subjects with a maximum increase from baseline in QTcB and QTcF intervals will be summarised for each treatment according to the following categories: >30, >60, and ≤ 30 ms. All incidences of >30 and >60 ms will be flagged on the listing. In addition, the frequency of subjects with QTcB and QTcF postdose values will be summarised for each treatment, according to the following

categories: >450, >480, >500, and \leq 450 ms. All incidences of >450, >480, and >500 ms will be flagged on the listing.

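### Repeats taken only after an abnormal reading replace that reading in the vital-sign and ECG summaries, and outside QTcB/QTcF the SAP text describes no by-treatment count of the originals

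*SAP*

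**What the plan says.** **When a repeat is taken.** The Day 1 predose vital signs (blood pressure and pulse) and ECGs are triplicates. For later readings, Protocol 7.3.3 says: "All subsequent measurements will be performed singly and repeated once if outside the relevant clinical reference ranges". Protocol 7.3.4.1 has the same rule for ECGs. It also calls for a repeat if QTcF exceeds 500 msec or if the "QTcF change from the baseline (predose) is > 60 msec".

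**What happens to it.** Under SAP 10.1.2, repeats "replace the original readings in all summaries and changes from baseline presentations and calculations". A postdose reading counts as a repeat if it falls within 15 minutes of the original. A later one is unscheduled and stays out of the summaries, so the original remains. The rule does not ask for a documented artefact.

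**The exception.** The outlier analysis in SAP 10.6.4 uses every individual postdose measurement, "including all repeat and unscheduled readings". Its scope is the corrected QT: "The frequency of subjects with a maximum increase from baseline in QTcB and QTcF intervals will be summarised for each treatment", plus absolute QTcB and QTcF categories.

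**Everything else.** SAP 10.6.3 says: "Vital signs values outside the clinical reference ranges will be flagged on the individual subject data listings". SAP 10.6.4 does the same for ECG parameters. Neither section describes a count by treatment for vital signs, PR, QRS, uncorrected QT or heart rate. Laboratory results get a little more, since in SAP 10.6.2 serum biochemistry, haematology and "urinalysis data outside the clinical reference ranges will be listed by parameter and treatment".

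**The concern.** A reading is re-measured because of its own value. In-range readings get no second measurement, so the substitution works in one direction, toward the reference range. It affects the minimum and maximum most, and SAP 10.1 plans to report both.

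Vital signs and 12-lead ECG parameters are primary endpoints (Protocol 2.2.1). They are assessed descriptively, with no inferential analysis (SAP 10.6.6). With six active subjects per cohort in Part A and eight in Part B, a reader comparing doses will look at the extremes and at how many subjects went out of range. Under the rule, an abnormal first reading can be absent from the tabulated maximum or minimum, and the SAP text offers no table by treatment that puts it back. Timing also matters: a confirmation at 14 minutes removes the original from the tables, and one at 16 minutes leaves it in.

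**Working it through.** The plan states no figure for this point, so there is nothing to reproduce. The direction follows from the text. The size needs inputs that the documents do not give, so every input below is an assumption.

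**Inputs (assumed), systolic pressure at one timepoint:** mean 118 mmHg; limits 90 and 140; between-subject SD b = 8 to 10; within-subject SD w = 5 to 8; true drug effect 0 or +10 mmHg. A share p of the within-subject variance persists to the repeat (p = 0, 0.5 or 0.75). Every out-of-range reading is replaced by one repeat within 15 minutes.

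**Mean.** Let s² = b² + w², and let μ be the true mean. Given a first reading x, the expected difference between original and repeat is (1 − p)(w²/s²)(x − μ). Averaging over out-of-range readings gives

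bias = −(1 − p)(w²/s)[φ(u) − φ(l)], with u = (140 − μ)/s and l = (90 − μ)/s.

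Example: b = 8, w = 8, p = 0, effect +10, so μ = 128.
- s = √(64 + 64) = 11.31
- u = 12/11.31 = 1.061 and φ(u) = 0.2273
- l = −38/11.31 = −3.36 and φ(l) = 0.0014
- bias = −(64/11.31)(0.2273 − 0.0014) = −1.28 mmHg

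**Extremes.** These come from simulating 200,000 cohorts of six per setting. The simulated mean bias agrees with the formula. Ranges run over the four (b, w) pairs.

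| Effect | Share persisting | Mean bias (mmHg) | Fall in maximum of six (mmHg) | Cohorts whose summarised maximum drops to 140 or below, among those with an original above 140 | Same, of all cohorts |
|---|---|---|---|---|---|
| 0 | none | −0.06 to −0.27 | 0.4 to 1.8 | 55 to 81% | 4 to 16% |
| 0 | half | −0.03 to −0.14 | 0.2 to 1.0 | 40 to 60% | 3 to 11% |
| 0 | three quarters | −0.01 to −0.07 | 0.1 to 0.5 | 28 to 43% | 2 to 8% |
| +10 | none | −0.47 to −1.28 | 1.4 to 3.3 | 31 to 53% | 19 to 32% |
| +10 | half | −0.24 to −0.64 | 0.7 to 1.7 | 21 to 35% | 13 to 21% |
| +10 | three quarters | −0.12 to −0.32 | 0.3 to 0.9 | 14 to 24% | 9 to 14% |

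At +10 mmHg, 10 to 18% of original readings are out of range. Among summarised readings the share is 5 to 11% with none or half persisting.

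**QTcF** (assumed mean 400 to 410, limit 450, b = 12 to 16, w = 6 to 10, p = 0 or 0.5). With the upper limit only, the formula gives 0 to −0.2 ms with no effect and 0 to −1.2 ms at +20 ms. The QTcF extremes are counted from all readings anyway.

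**What pulls these figures down.** Original and repeat are at most 15 minutes apart, so high persistence is plausible. At p = 0.9 the +10 mmHg bias is one tenth of the p = 0 row, about −0.05 to −0.13 mmHg. Confirmations after 15 minutes leave the original in place, so the table is an upper bound on that point.

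**The case against.** The strongest reply is that this is a convention rather than an error. A repeat is taken because the result needed confirmation. A normal second reading minutes later is some evidence that the first was not sustained, so part of the fall in the maximum is removal of momentary noise. The rule is prespecified, applies to every treatment, and operates in a double-blind study. That stands, and it is a good reason to leave the main summaries alone. It does not remove the selection, because only abnormal readings get a second chance. A count over all readings needs no ruling on which reading was right.

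A reader might infer that the extremes disappear from the report. The documents do not support that. Repeats are labelled and out-of-range values flagged in the listings, and with cohorts this small the listings can be read through. A reader might also infer that subject safety or dose escalation is compromised. It is not: Protocol 3.6 has the Investigator review all available blinded data, treatment-emergent adverse events are tabulated (SAP 10.6.1), and QTcB and QTcF have their own all-readings tables.

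Nor can it be said that no table anywhere counts these readings. SAP 4 places the detailed outputs in a separate shell document, which was not available. The supportable statement is that the SAP text describes none.

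**Conclusion.** The point holds as a reporting improvement to consider. The replacement depends on the value of the first reading, and for primary safety endpoints other than QTcB/QTcF the SAP text provides no count by treatment to set beside the summaries.

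The bias in means is small: at most about 0.3 mmHg with no drug effect, and about 0.1 to 1.3 mmHg at a true +10 mmHg, depending on how much within-subject variation persists to the repeat. It would be wrong to conclude that the rule would mask a real mean effect; even the least favourable setting takes 1.3 mmHg off 10. The clearer effect is on exceedances. At +10 mmHg, 14 to 53% of cohorts with an original above 140 would show a summarised maximum at or below it.

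All of these sizes rest on assumed SDs, limits and effects for one parameter at one timepoint. The true size in this trial cannot be derived from the documents.

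**What to change.** Extend the all-readings count of SAP 10.6.4 to vital signs, PR, QRS and heart rate. For each treatment, give the number of subjects with any out-of-range postdose value over original, repeat and unscheduled readings, using the reference ranges already used for flagging. Uncorrected QT can be left to the existing QTcB and QTcF counts. If the table shells already contain such a table, one sentence in SAP 10.6.3 and 10.6.4 closes the point.

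Keep the repeat convention for the main summaries. A parallel set of means on original readings is not needed, because the means barely move. A technical-failure exception would need a recorded reason for each repeat, and the documents describe no field for one. Baseline can stay as it is ("Where results are taken in triplicate and repeated, the last 3 readings are used in all subsequent calculations"), since predose repeats shift the mean baseline by only 0.01 to 0.11 mmHg under the blood-pressure assumptions with none or half persisting.

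The cost is SAP wording and one or two tables from data already held. The downside is that an occasional artefactual first reading will be counted; a footnote can say that the table includes unconfirmed values.
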